9.3.2. Curated Data

Data abstracted by Clinical Research Nurses (CRNs) will include the following:

1. Race/Ethnicity.
2. Date of initial diagnosis of breast cancer.
3. Stage at initial diagnosis of breast cancer.
4. Modalities of treatment received at any point prior to A/MBC diagnosis (Surgery, Radiation, Chemotherapy, Hormone therapy). This variable will be collected as “Yes” or “Not Documented” for each modality. The last date of systemic therapy, including hormonal therapy, administered in the adjuvant setting prior to stage IV/MBC diagnosis will be documented, if applicable.
5. Among patients who have a record of hormone therapy prior to A/MBC diagnosis, the name(s), and start and end dates of the hormonal agents received in the adjuvant setting will be collected.

6. Status of the patient as having progressed at any point after initiation of the first hormone therapy in the adjuvant setting, prior to A/MBC diagnosis (Y/N). If yes, the date of first disease progression/recurrence following initiation of hormone therapy in the adjuvant setting will be collected.
7. Date of A/MBC diagnosis. This date defines the index date for the study, as referenced below in describing other study variables.
8. Stage at index date (IIIB, IIIC, or IV).
9. For patients documented as Stage IIIB or IIIC at index date, the date of Stage IV/metastatic diagnosis will be collected, if applicable, from the index date through the end of the record or the end of the study, whichever occurs first.
10. Sites of distant metastasis at index date, if applicable (Bone; Chest Wall; Contralateral Breast; Distant Lymph node(s); Liver; Lung; Peritoneum; Pleural nodules; Malignant pleural effusion; Skin; Brain; Undocumented; Other, Specify).
11. Disease histology (Adenoid cystic; Cribriform; Ductal; Inflammatory; Intraductal; Lobular; Medullary with lymphoid stroma; Medullary, NOS; Mucinous; Paget's disease and infiltrating; Paget's disease and intraductal; Papillary; Secretory; Squamous cell; Tubular; Undifferentiated; Undocumented, Other, specify) nearest in time to index date.
12. ER status nearest in time to index date.
13. PR status nearest in time to index date.
14. HER2 status nearest in time to index date.
15. Menopausal status (Pre, Peri, Post, UD) nearest in time to the date of, but before, index date. Date of documentation will be collected.
16. ECOG/performance status, if available or indication of impaired performance status not otherwise classified as an ECOG rating, at index date (± 60 days). Where available, Karnofsky performance status will be converted to corresponding ECOG score.
17. Comorbidities, indicated as present vs. not indicated as present at index date. The conditions and date of the condition to be assessed will include those assessed as part of the standard Charlson Comorbidity Index. These include myocardial infarction, congestive heart failure, peripheral vascular disease, cerebrovascular accident, hemiplegia, chronic obstructive pulmonary disease, ulcer disease, diabetes, renal disease, connective tissue disease such as rheumatoid arthritis or lupus, Alzheimer's or other dementia, cirrhosis or other serious liver disease, leukemia, lymphoma, metastatic solid tumor (other than breast cancer), and HIV/AIDS.

PFIZER CONFIDENTIAL

18. Other comorbidities of interest, indicated as present vs. not indicated as present at index date: hypertension and hyperlipidemia.
19. Dates of disease progression after index date through the end of the record or the end of the study, whichever occurs first.
20. Documentation of treatment modifications (dose modification, schedule changes, dose delay, hold, or discontinuation) for palbociclib, **CCI** [REDACTED] and reasons for treatment modifications, if applicable, from the index date through the end of the record or the end of the study, whichever occurs first. Date of treatment modification and reason for modification will be collected, if available.
 - Reasons for modification will include: Cost, disease progression, patient refusal/request, toxicity (specify), other (specify), or UD.
21. Oral anti-cancer therapies. This will include all treatments from the index date through the end of the record or the end of the study, whichever occurs first. **CCI** [REDACTED]
22. Documentation of any IV, IM, or subcutaneous anti-cancer therapy not otherwise documented in standard medication tables, including all treatments received from the index date through the end of the record or the end of the study, whichever occurs first. Agent and start and end dates will be collected.
23. First positive response and best overall response for each regimen from the index date through the end of the first progression-based line of therapy containing the first qualifying endocrine-based therapy, the end of the record or the end of the study, whichever occurs first. Responses will be classified as Complete response (CR); Partial response (PR); Stable disease (SD); Progressive disease (PD); Not evaluable (NE); or Undocumented. The date of the first positive response (CR or PR) and of the best overall response for each regimen will be collected.

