9.2. Setting

9.2.1. Inclusion Criteria

Patients must meet all of the following inclusion criteria to be eligible for inclusion in the study:

1. Female or male sex.

PFIZER CONFIDENTIAL

[REDACTED]

2. Diagnosis (confirmed by clinical review) of A/MBC, defined as breast cancer at stage IIIB, stage IIIC, stage IV or identified as having distant metastasis.
3. Age ≥ 18 years at A/MBC diagnosis.
4. Initiated a CDK4/6i in combination with an AI as initial endocrine-based therapy after A/MBC diagnosis on or after 2/3/2015 and before 4/1/2019.
 - Note that the date of the start of the inclusion period reflects the month that the first CDK4/6i (ie, Palbociclib) received U.S. FDA approval.
5. Evidence of ER or PR positive disease, or absence of any indication of ER and PR negative disease closest to A/MBC diagnosis (ie, patients are eligible without affirmative indication of ER/PR+ status as long as ER/PR- indication is not present).
6. Evidence of HER2 negative disease, or absence of any indication of HER2 positive disease closest to A/MBC diagnosis (ie, patients are eligible without affirmative indication of HER2- status as long as HER2+ indication is not present).

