4.2. Subgroups

Summaries of study outcomes may be repeated focusing alternatively on but not limited to the following subgroups of interest—sample size permitting—which will be defined on the basis of:

- Age (years): ≤ 50 , 51-64, 65-74, ≥ 75 ;
- Gender, if number of males is low then we can restrict results to females;
- Race: White, Black, Other;
- Disease stage at initial diagnosis: I or II, III, IV;
- ECOG performance status: 0, 1 or 2, ≥ 3 ;
- Site of metastasis: Visceral, Non-visceral, Bone only;
- Number of metastatic sites: 1, 2, ≥ 3 ;

PFIZER CONFIDENTIAL

- Menopausal status: premenopausal, perimenopausal, Postmenopausal, undocumented;
- Hormone therapy prior to A/MBC diagnosis: yes, no;
- Chemotherapy prior to A/MBC diagnosis: yes, no;
- Surgery prior to A/MBC diagnosis: yes, no;
- Radiation therapy prior to A/MBC diagnosis: yes, no;
- Disease free interval: ≤ 12 months, > 12 months;
- Starting dose: by starting dose levels for Palbociclib, CCI

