5.1. DEMOGRAPHIC AND CLINICAL CHARACTERISTICS

Variable	Operational definition
Demographic characteristics	
Age	Age at A/MBC diagnosis, years
Age category	≤ 50 , 51-64, 65 –74, ≥ 75 years
Sex	Female or Male
Race	White, Black, Asian, Other, Unknown
Region of residence	Based on state where the patient resides: Northeast, Midwest, South, West
Insurance status	Private only, public only, public and private, or neither reported at index date and reported at initiation of the earliest endocrine-based therapy after the index date.
Clinical characteristics	
Menopausal status	(Pre, Peri, Post, UD) nearest in time to the date of, but before, index date.
Type of MBC	De novo MBC (newly diagnosed): Stage 4 at initial BC diagnosis Recurrent MBC: Stages 0-3 at initial BC diagnosis
Modalities of treatment received at any point prior to A/MBC diagnosis	Surgery (yes/no), Radiation (yes/no), Chemotherapy (yes/no), Hormone therapy (yes/no)

PFIZER CONFIDENTIAL

ECOG performance score	ECOG performance at index date (\pm 60 days), 0, 1,2,3,4,5, or missing. Where available, Karnofsky performance status will be converted to the corresponding ECOG score.
Disease stage at initial BC diagnosis	Stage I, II, III, IV, unknown/ undocumented
Disease stage at index date (date of A/MBC diagnosis)	IIIB, IIIC, or IV
Time from initial BC diagnosis to first MBC diagnosis	Months from the date of initial BC diagnosis to the date of metastatic diagnosis.
Disease free interval	The number of months between completion of adjuvant therapy and diagnosis of A/MBC.
Sites of distant metastasis at index date	Bone; Chest Wall; Contralateral Breast; Distant Lymph node(s); Liver; Lung; Peritoneum; Pleural nodules; Malignant pleural effusion; Skin; Brain; Undocumented; Other Specified. All sites will be reported as (yes/no).
Visceral metastasis at index date	Metastasis at one or more of the following sites: liver, pancreas, intestines, lung, heart, malignant pleural effusion, peritoneum, pleura. Other metastasis sites, including bone or non-visceral metastasis, may be present.
Non-visceral metastasis at index date	Metastasis at one or more of the following sites: bone, brain, skin, chest wall, contralateral breast, or distant lymph nodes.
Bone-only metastasis at index date	Bone metastasis, with no metastasis at any other identified site

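### Menopausal status is taken only from entries before the A/MBC diagnosis date, so valid entries at diagnosis are discarded and the undocumented level will tend to track newly diagnosed advanced disease

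*Protocol*

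**What the plan says.** Protocol 9.3.2 item 15 collects "Menopausal status (Pre, Peri, Post, UD) nearest in time to the date of, but before, index date". It adds "Date of documentation will be collected". SAP 5.1 carries the same rule in the same words. Item 7 fixes the reference point: "Date of A/MBC diagnosis. This date defines the index date for the study". Neither document limits how far back an entry may lie.

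Objective 1a (Protocol 8, SAP 2.2) lists menopausal status among the characteristics to be described as of A/MBC diagnosis. Neighbouring items are looser on timing. Item 14, for example, is "HER2 status nearest in time to index date", with matching rules for histology, ER and PR (items 11 to 13). Item 16 accepts ECOG within 60 days on either side.

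A/MBC is "defined as breast cancer at stage IIIB, stage IIIC, stage IV or identified as having distant metastasis" (Protocol 9.2.1). SAP 5.1 defines "De novo MBC (newly diagnosed): Stage 4 at initial BC diagnosis". SAP 4.2 lists the subgroup "Menopausal status: premenopausal, perimenopausal, Postmenopausal, undocumented". Table 2a reports menopausal status with female patients as the denominator.

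**The concern.** The operational rule does not measure what the objective names. It leaves out the day of diagnosis and everything after it, and it accepts a value of any age from before. No reason is given for treating this variable differently from its neighbours.

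The loss is unlikely to be random. For a woman first diagnosed at stage IV, IIIB or IIIC, the index date is in principle her first breast cancer diagnosis, so the rule looks only at the time before her cancer was diagnosed. The undocumented level would then partly stand in for newly diagnosed disease. SAP 4.2 allows outcomes to be summarised at that level, SAP 7.2 uses no covariates and SAP 6 imputes nothing, so nothing in that summary would separate the two.

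For a recurrent patient the problem runs the other way. A pre- or perimenopausal entry from the original diagnosis may be counted as her status at A/MBC diagnosis.

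**Working it through.** There is no figure in the plan to reproduce. The check is a comparison of rules, followed by an illustration with labelled assumptions.

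**1. Timing.** Let t be the entry date minus the index date.
- Objective 1a: status at t = 0.
- Item 15 and SAP 5.1: the latest entry with t < 0, with no lower limit.
- Histology, ER, PR, HER2: smallest |t|, either sign.
- ECOG: |t| ≤ 60 days.

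An entry at t = 0 or t = +1 day is rejected for menopausal status but would be accepted under every neighbouring rule.

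**2. Who loses entries.** For women first diagnosed at stage IV, IIIB or IIIC, t < 0 means before the first breast cancer diagnosis. Protocol 9.4 describes the source as the medical oncology record. That such a record usually opens around diagnosis is an assumption; the documents do not say when records begin.

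**3. Size of the rule's effect.** The rule is responsible only for women with no entry before index and a usable entry on or shortly after it:

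A = s·m·u + (1 − s)·m′·u′

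Here s is the share of women whose index date is their first diagnosis, m the share of them with no pre-index entry, and u the share of those with a usable entry on or shortly after index. Primes denote the same quantities in other women. The documents give none of these. Setting the second term to zero and assuming s = 0.20 to 0.40, m = 0.10 to 1.00, u = 0.60 to 1.00:
- low: 0.20 × 0.10 × 0.60 = 0.012, or 1.2% of women
- high m, u = 0.60: 0.40 × 1.00 × 0.60 = 0.24, or 24%
- upper limit: 0.40 × 1.00 × 1.00 = 0.40, or 40%

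A span of 1.2% to 40% shows that the size is unknown; it is not an estimate. The number of women is not given either, so no head count follows.

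**4. Who makes up the undocumented level.** With an assumed undocumented share r = 0.20 among other women, the fraction of that level who are newly diagnosed is s·m / [s·m + (1 − s)·r]:
- s = 0.20, m = 0.50: 0.10 / (0.10 + 0.16) = 0.38, against 0.20 among all women
- s = 0.40, m = 1.00: 0.40 / (0.40 + 0.12) = 0.77, against 0.40 among all women

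The level over-represents newly diagnosed women whenever m exceeds r, and does not when m = r.

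**5. Age of the value.** The documentation date is collected, but no visible rule or table shell uses it. It can expose an old value. It cannot recover an on-index or later entry that abstractors were told not to record.

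**The case against.** Several points on the other side stand.

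- A reader might infer that every de novo patient must end up undocumented. The documents do not support that. Protocol 9.4 describes an essentially complete oncology record, and a work-up, referral or history note dated before the recorded diagnosis would qualify. The effect is likely, not certain.
- A reader might multiply an assumed de novo share by an assumed share lacking a pre-index note and ascribe the whole product to the rule. That also counts women with no entry anywhere, who would be undocumented under any rule. Applying it to the whole cohort of 1,100 to 1,300 would also include men, whom Table 2a leaves out of this percentage.
- A reader might conclude that the subgroup is spoiled. That is too strong. Subgroup summaries are optional and depend on numbers, the study tests no hypotheses, undocumented is an explicit level, and type of MBC is tabulated separately.
- Old values are not peculiar to this item: histology and receptor status have no look-back limit either. A past postmenopausal entry normally stays valid, so the risk is confined to old pre- and perimenopausal entries.
- A pre-index rule protects the baseline, because treatment given after diagnosis can alter menopausal status. Accepting every entry up to the start of endocrine-based therapy would lose that protection where other treatment came first.

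The last point limits the fix. It does not justify rejecting an entry made on the day of diagnosis or soon after, before any treatment. The mismatch with Objective 1a remains.

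**Conclusion.** The point holds as a defect in one baseline variable under a primary descriptive objective. As written, the rule discards valid entries made on or just after A/MBC diagnosis. It is likely to raise the undocumented share among women first diagnosed at stage IV, IIIB or IIIC, and it may count outdated pre- or perimenopausal entries as current for recurrent patients.

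The mismatch in timing is plain from the text. The uneven loss rests on the assumption that oncology records usually begin around diagnosis. The size cannot be stated from the documents and should be measured in the data. The overall rwPFS, OS and rwTR results do not use this variable and are unaffected; only the Table 2a description and the optional subgroup summaries are. The change is worth making because it is cheap early and hard to make later.

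**What to change.** Change item 15, SAP 5.1 and the abstraction instruction together:

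1. Take the entry closest to the index date, counting the index date itself and a short window around it. The 60 days either side already used for ECOG would serve.
2. Accept a post-index entry only if it precedes any post-index anti-cancer treatment.
3. Use an earlier pre-index entry only if the window holds none.
4. Report the interval from documentation to index, and tabulate undocumented status by de novo and recurrent disease among female patients. SAP 5.1 classes stage 0 to 3 at first diagnosis as recurrent, so IIIB/IIIC first diagnoses fall there. A further split by whether the index date equals the initial diagnosis date (items 2 and 7) would show them.

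If the present rule must stay reproducible, also record the last pre-index entry and its date.

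The cost is a short wording change while abstractors are reading the same notes. Once charts have been abstracted under the present rule, it means reopening them. The downside is that a few values will be dated shortly after diagnosis.

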9.3.3. Extracted Data

Patient data from OncoEMR will be flagged to be excluded from the regulatory study. Data extracted from the Definitive Oncology Dataset through SQL query will include the following:

1. Sex.
2. Insurance status (private only, public only, public and private, or neither) at index date and at initiation of the earliest endocrine-based regimen after the index date.
3. Date of birth.

[figure not shown]
4. Date of death, as indicated in the clinical record and by Social Security Death Index (SSDI) records or associated obituary records linked to the Definitive Oncology Dataset.
5. Treatments and dates of treatments for all infused or injected anti-cancer therapies from the index date through the end of the record or the end of the study, whichever occurs first.

9.3.4. Derived Variables

Variables suggested to be derived for this study's purpose will be generated by Pfizer analytical team. Final algorithm to derive the variables will be further determined by Pfizer. The suggested variables derived from abstracted and extracted data will include the following:

1. Age at index date, at initiation of the earliest endocrine-based regimen, and at first treatment regimen after the index date.
2. Weighted index of comorbid disease condition. Weighting of comorbid conditions (not including breast cancer) will follow the weighting as specified in the Charlson Comorbidity Index.
3. Start and end dates of anti-cancer treatments from the index date through the end of the record or the end of the study, whichever occurs first.
4. Treatment regimens, derived from oral and infused agents delivered, including start and end dates.
5. Endocrine sensitivity prior to the index date, defined as endocrine sensitive vs. resistant vs. refractory based on adjuvant endocrine therapy experience. Endocrine sensitive: ≥24 months without recurrence/progression after completion of endocrine therapy in the adjuvant setting; Endocrine resistant: recurrence/progression after completion of endocrine therapy, and within 24 months of completion of endocrine therapy; Endocrine refractory: recurrence/progression while on endocrine therapy in the adjuvant setting, defined as occurring while on or within <30 days after discontinuation of endocrine therapy. The 30 day window allows that endocrine therapy may be discontinued because of a perceived progression before that progression is actually documented.
6. Primary endocrine resistance defined as a relapse while on the first 2 years of adjuvant endocrine therapy or disease progression within the first 6 months of first-line endocrine therapy for A/MBC, while on endocrine therapy.

PFIZER CONFIDENTIAL

7. Secondary (acquired) endocrine resistance defined as a relapse while on adjuvant endocrine therapy but after the first 2 years or a relapse within 12 months of completing adjuvant endocrine therapy, or disease progression ≥ 6 months after initiating endocrine therapy for A/MBC, while on endocrine therapy.

9.4. Data Sources

The present study will include data from Patient360 and other curated data available within the Definitive Oncology Dataset.

The Definitive Oncology Dataset is drawn from a wide range of principally community oncology practices throughout the United States. Practices range in size from very small to large, and are located in both rural and urban settings. The practices are not all members of any one group purchasing organization, so practice patterns reflect real-world variability of treatment.

Datasets available to Concerto HealthAI include a repository of oncology healthcare data, including those from practices affiliated with CancerLinQ - a wholly-owned subsidiary of the American Society of Clinical Oncology that works with both nonprofit and federal agencies to warehouse and aggregate medical records of cancer patients treated at practices in 40 U.S. states and the District of Columbia - as well as administrative healthcare claims and genomic data.

Key features of the Definitive Oncology Dataset include the following.

- Availability of both structured data (tables, rows and columns) and unstructured data (text and image documents, eg, physician progress notes). The unstructured information is generally not available in other Electronic Medical Record (EMR) data sources, although this is where much of the richest clinical information is found. Together with the structured data, Concerto HealthAI has access to an essentially complete version of the medical oncology health record for each patient. As a result, analysis does not need to rely on proxy measures of key clinical endpoints, as may be the case where only structured EMR data are available.
- Treatment across the practices from which data are drawn is not directed by any single group purchasing organization requirements, unlike some other providers of EMR data. Therefore, data from the Concerto HealthAI network reflect the diversity of real-world independent practice.
- The real-world diversity of the practices from which data are drawn, and the clinical depth of the information available, enable our experienced oncology research team to answer study questions that cannot be addressed through other data sources.

9.5. Study Size

The study will include all patients (estimated 1100 –1300 patients) in the data set for the descriptive elements who meet the inclusion/exclusion criteria.

CCI

[REDACTED] The sample size of this study will be based on the actual number of eligible patients available for the study through CRN screening.

Given the inclusion criterion requiring a qualifying diagnosis of HR+/HER2- A/MBC between 2/3/2015 to 4/1/2019, and assuming data collection were to start by 12/1/2019, the average follow-up available for patients receiving Palbociclib plus AI combination therapy is therefore $((50/2) + 8) = 33$ months.

9.6. Data Management

Following preparation and institutional review board (IRB) approval of a study protocol, updated SQL queries will be written to identify patients within the Definitive Oncology Dataset with evidence of diagnosis of the disease of interest. Feasibility programming has already identified likely eligible patients. However, some refinement of this programming will be undertaken to enhance identification of eligible patients. The resulting program will be used to populate a screening list used by Concerto HealthAI research staff for review of the electronic medical records.

Concerto HealthAI's Statistical Group will extract information related to demographic characteristics, infused treatments, staging, and other clinical data, as applicable. Experienced CRNs will examine the medical record of each potentially eligible patient. The disease of interest and other eligibility criteria will be verified and documented. If the patient meets all eligibility criteria, the patient will be accrued. For each eligible patient, the relevant study data will be extracted by SQL query or abstracted by CRNs onto case report forms and entered into a secure database for analysis.

CCI

[REDACTED]

[REDACTED]

[REDACTED]

